STUDY NAME: CLINICAL EVALUATION OF SAFETY AND EFFICACY OF RADIO-FREQUENCY ASSISTED LIPOLYSIS (RFAL) OF BREAST ENVELOPE AND NIPPLE-AREOLAR COMPLEX (NAC) POSITION

Date:

August 2018

Identifiers: NCT03863834 Unique Protocol ID: D0607738

I N M O D E
aesthetic solutions

Clinical Evaluation of Safety and Efficacy of Radio-Frequency Assisted Lipolysis (RFAL) of Breast Envelope and Nipple-Areolar Complex (NAC) Position

Protocol No:
DO607738A

Rev. Date: August, 2018

SIRB ID: 6254

STUDY NAME: CLINICAL EVALUATION OF SAFETY AND EFFICACY OF RADIO-FREQUENCY ASSISTED LIPOLYSIS (RFAL) OF BREAST ENVELOPE AND NIPPLE-AREOLAR COMPLEX (NAC) POSITION

Date: August 2018

Protocol No: D0607738

Revision No.: B

Sponsor: InMode MD Ltd.

[name]
[name]
[name]
[name]
[contact]
[contact]

INMODE

aesthetic solutions

Clinical Evaluation of Safety and Efficacy of Radio-Frequency Assisted Lipolysis (RFAL) of Breast Envelope and Nipple-Areolar Complex (NAC) Position

Protocol No:
DO607738A

Rev. Date: August, 2018

SIRB ID: 6254

APPROVALS:

	Name	Title	Signature	Date
Written by:	[name]	CLINICAL MANAGER		
Edited by:	[name]	VP, RESEARCH AND COMPLIANCE		
Approved by:				

Revision Log:

Revision #	Date	Modification
A		First Release
B	8.8.18	

INMODE
aesthetic solutions

Clinical Evaluation of Safety and Efficacy of Radio-Frequency Assisted Lipolysis (RFAL) of Breast Envelope and Nipple-Areolar Complex (NAC) Position

Protocol No:
D0607738A

Rev. Date: August, 2018

SIRB ID: 6254

PROTOCOL SYNOPSIS

Study Title	CLINICAL EVALUATION OF SAFETY AND EFFICACY OF RADIO-FREQUENCY ASSISTED LIPOLYSIS (RFAL) OF BREAST ENVELOPE AND NIPPLE-AREOLAR COMPLEX (NAC) POSTION
Study Number	D0607738A
Principal Investigators	[name]
Study Design	This is a single center clinical study to determine the safety and efficacy of using Radiofrequency (RF) energy for minimally invasive breast lift procedure. Treatment areas will include breast area.
Study Sites / Country	[name] Maxwell Aesthetics [name]
Planned Study Duration	Study duration including recruitment will be up to 18 months.
Investigational Product	The InMode RF™ platform has been cleared by the United States Food and Drug Administration (FDA) (K151793) for use in dermatological and general surgical procedures for electrocoagulation and hemostasis.
Planned Sample Size	Up to 10 adult subjects

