At the first visit, the Investigator will discuss with the subject the various treatment alternatives for a Breast Ptosis, both non-surgical and surgical, including the minimally invasive RF and other treatment modalities.

VISIT 1:

SCREENING

During the first visit, the investigator or a representative on his behalf will obtain an Informed Consent Form (ICF) from the subject, clearly indicating his/her understanding of the requirements and risks involved with study participation.

Possible adverse effects include but not limited to bleeding, infection, scarring, skin contour irregularities, thermal trauma to the skin, asymmetry, scarring, surgical shock, pulmonary complications, skin loss, seroma, allergic reaction, and anesthesia related complications can occur and should be discussed and understood. The subject must understand the importance of pre-treatment and

	Clinical Evaluation of Safety and Efficacy of Radio-Frequency Assisted Lipolysis (RFAL) of Breast Envelope and Nipple-Areolar Complex (NAC) Position	
	Protocol No: DO607738A SIRB ID: 6254	Rev. Date: August, 2018

post-treatment instructions and that failure to comply with these instructions may increase the probability of complications.

The Investigator will obtain a focused subject medical history including exclusion criteria specified herein and the front, back and both sides of the treatment area using a high resolution digital camera, as well as additional information that is specified in the case report form.

The follow-up visits should be scheduled 1 week, 6 weeks, 3 months, 6 months and optional 12 months after the treatment.

Photographs should be taken prior to the baseline treatment and at each of the follow-up visits, as well as Vectra 3D Imaging and static measurements. Participants must have a recorded mammogram prior to the first treatment. All measurements will be recorded on the case report form (CRF).

VISIT 2:

TREATMENT

The treatment will be performed once. The treatment procedure should be conducted according to the following guidelines:

INMODE
aesthetic solutions

Clinical Evaluation of Safety and Efficacy of Radio-Frequency Assisted Lipolysis (RFAL) of Breast Envelope and Nipple-Areolar Complex (NAC) Position

Protocol No:
DO607738A

Rev. Date: August, 2018

SIRB ID: 6254

Treatment Parameters

Treatment area	Treatment depth	Hand Piece	External Cut-off Temperature	Internal Cut-off Temperature	Treatment time

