- A prophylactic antibiotic regimen may be prescribed for subjects starting one day before treatment until one-week post-treatment according to physician discretion. Prophylactic antibiotics should be administered on the day of treatment and continued for a minimum of 2 doses following the RAL procedure.
- Discomfort can be reduced by cool compresses or standard post-operative analgesic.
- Compression garments may be used for up to 6 weeks.
- Appropriate vigorous exercise restrictions should be instituted.
- Subject is to contact physician if there is any indication of infection, fever, excessive swelling, redness, undue pain, shortness of breath, swelling of the ankles, chest pain, irregular heart beat or any other unusual or untoward symptom.

I N M O D E
aesthetic solutions

Clinical Evaluation of Safety and Efficacy of Radio-Frequency Assisted Lipolysis (RFAL) of Breast Envelope and Nipple-Areolar Complex (NAC) Position

Protocol No:
DO607738A

Rev. Date: August, 2018

SIRB ID: 6254

SAFETY AND RESULT MEASUREMENTS

Photography

At each of the specified time points (before the treatment and at the follow-up visits), photos of the body should be taken, including a frontal photo, back photo and two side images of the body from knee up to breast line as it is shown in the picture on the next page. Hands of the subject should be at the side of the body in the position that does not block and does not shade the treated area.

The photos should be taken under controlled conditions, including the colour of the background material, distance from the camera, angle and lighting, including flash, in order to achieve consistent, high-quality before & after pictures. Each picture should be accompanied with the date, visit number, subject ID, subject initials.

Vectra 3D Photography

3D photography of the breast region will be taken in all patients during the routine preoperative work-up using a commercial 3D scanner, VECTRA XR scanner (Canfield Scientific). Patients will be asked to stand with their arms in varying positions and each scanning takes approximately 1–2 seconds. Photographs will be created in both standard format and pixelated format to highlight surface contour.

Weight

Subject weight measurements should be taken before the treatment and at each follow-up visit.

Static Measurements

Additional evaluation of changes in breast shape, including upper pole fullness, breast projection, and bottoming out will be assessed by static measurements:

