- Sternal Notch to Nipple
- Nipple to IMF
- Base Width (at point of breast take off from chest wall)

INMODE
aesthetic solutions

[figure not shown]
Clinical Evaluation of Safety and Efficacy of Radio-Frequency Assisted Lipolysis (RFAL) of Breast Envelope and Nipple-Areolar Complex (NAC) Position

Protocol No:
DO607738A

Rev. Date: August, 2018

SIRB ID: 6254

- Nipple to nipple.

1. Base width (BW)
2. Nipple to inframammary fold distance (N-IMF)
3. Intermammary distance
4. Sternal notch to nipple distance (SN-N)
5. Soft tissue pinch test (PT)
6. Maximum skin stretch (MSS)

EVALUATION

Three independent plastic surgeons will evaluate photographs of the preoperative and postoperative photographs at 3-, 6- and if applicable, 12-month results.

DISCONTINUATION

Subjects enrolled in the study will be free to discontinue their participation in the study at any time. A decision to discontinue participation will not prejudice their medical care. In those instances, Investigators will attempt to obtain clinical results and side effect evaluation concerning the subject prior to his/ her withdrawal.

INMODE
aesthetic solutions

Clinical Evaluation of Safety and Efficacy of Radio-Frequency Assisted Lipolysis (RFAL) of Breast Envelope and Nipple-Areolar Complex (NAC) Position

Protocol No:
DO607738A

Rev. Date: August, 2018

SIRB ID: 6254

DATA ANALYSIS

Statistical analysis of all major body factors will be performed to determine quantitatively the treatment efficacy.

The data will be analysed by the Sponsor using basic descriptive statistics, as well as comparison tests, where applicable. Treatment-related complications will be monitored and reported; if applicable, their incidence rate will be calculated and analysed for any relationship to treatment parameters and/or skin type.

RISK/BENEFIT ANALYSIS

RISKS

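### The 2D photographs are framed with the breast as the upper limit, so the three independent surgeons are not assured of images showing nipple position against a fixed landmark

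*Combined protocol and SAP*

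**What the plan says.** The synopsis (Study Design) names one area: "Treatment areas will include breast area". Two places then describe the standard photographs.

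- **Safety and Result Measurements, Photography:** photographs before treatment and at follow-up, "including a frontal photo, back photo and two side images of the body from knee up to breast line". The sentence ties this frame to a reference picture ("as it is shown in the picture on the next page"). The subject's hands are to be "in the position that does not block and does not shade the treated area". Conditions are to be controlled, including "distance from the camera, angle and lighting, including flash".
- **Clinical Procedure, Visit 1 Screening:** "the front, back and both sides of the treatment area using a high resolution digital camera".

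The Evaluation section says: "Three independent plastic surgeons will evaluate photographs of the preoperative and postoperative photographs at 3-, 6- and if applicable, 12-month results". It does not say whether these are the standard photographs, the Vectra output or both, and it gives no rating scale or landmark.

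The Study Objectives rest on Vectra 3D imaging. The Static Measurements list includes sternal notch to nipple distance. Appendix I schedules both at all seven visits.

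**The concern.** A frame running from the knee to the breast suits contouring of the abdomen, flank or thigh. Here the breast is the object of study, yet it marks the border of the image. A surgeon comparing before and after pictures needs the whole breast in view and a landmark that the treatment does not move. The protocol uses the sternal notch for this when it measures nipple height by tape, but the photographic instruction does not ask for the notch to be shown.

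The study is open label with a single arm, and the sponsor analyses the data. Satisfaction and assessment forms are completed by the patient and the investigator, who both know that treatment was given. The three surgeons are the only assessors described as independent. If their images are poorly framed, the independent visual evidence is weakened, and a baseline photograph cannot be retaken after treatment.

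**Working it through.** The plan gives no figure to reproduce, so the check is textual.

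**1. What the upper edge includes.** Breast line is undefined, so the possible readings are set side by side.

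| Reading of breast line | Sternal notch required in frame? | Upper breast required in frame? | Upper edge could move with the outcome? |
|---|---|---|---|
| Top of the breast | No | Yes | Not evidently |
| Nipple level | No | No | Yes, if the camera is re-aimed at each visit |
| Inframammary fold | No | No | Possibly, if the camera is re-aimed at each visit |

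Only the first column gives the same answer in every row: the sternal notch is never required. The other two columns depend on the reading.

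**2. Agreement between sections.** The screening text takes the treatment area as the subject of the picture. The Photography section takes the body below the breast line. A site cannot tell from the text whether to centre the breast or to place it at the top edge. The rule on hand position shows that the treated area is meant to be visible, but it governs the hands and not the frame.

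**3. What is held constant.** Distance, angle and lighting are listed. Camera height is not named, although the list is introduced as examples.

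**4. Link to the surgeons.** The Evaluation section refers only to photographs, and the section with that title carries this frame. However, the Vectra section also calls its output photographs, in a standard and a pixelated format. The documents do not settle which set is rated.

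**5. Extent.** The inputs are up to 10 women (synopsis), 7 visits (Appendix I) and 4 views (Photography).

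- All standard photographs: 10 × 7 × 4 = 280 at most, including the optional 12-month visit.
- Those at time points the surgeons compare, taking one preoperative set per woman: 10 × 3 × 4 = 120 (preoperative, 3 and 6 months), or 10 × 4 × 4 = 160 with 12 months.

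These counts show how widely the rule applies. They do not measure lost information. The documents give no frame size, expected lift or rating error from which a loss of detectability could be calculated.

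**The case against.** The strongest case on the other side has four parts.

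- **The reference picture.** The frame is defined partly by a picture that is not in the available text, and its absence is not a fault of the plan. If it places the line at the top of the breast, nothing of the breast is lost. This stands. A reader might infer that the photographs cut off the upper breast, but the documents do not establish it.
- **Controlled conditions.** Distance and angle are controlled and the lower edge is at the knee, so fixed landmarks remain lower in the picture. A reader might infer that the frame rises with the breast and hides the lift. That would need both a nipple or fold reading and re-aiming of the camera at each visit, and neither is stated.
- **The image set.** The surgeons are not limited to the standard photographs. A reader might infer that they cannot see nipple lift. This does not follow, because Vectra images of the breast region are taken before treatment and at follow-up and could be part of what they rate.
- **The main measurements.** The objective rests on Vectra, and nipple height is measured directly. Neither uses this frame. This stands, and it limits the harm.

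The objection does not remove three facts. The notch is not required on any reading, the two sections describe the frame differently, and nothing says that the surgeons receive the Vectra images. The sternal notch to nipple distance is recorded on the case report form and is not a rating by an independent assessor.

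**Conclusion.** The concern holds in a limited form. The written frame does not suit a breast and nipple-position outcome and conflicts with the screening text. It leaves the independent surgeons without assured images of nipple position against a fixed landmark. Cropping of the upper breast is possible but depends on an undefined term.

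The effect is confined to the photographic evaluation. Nipple position is still captured by Vectra and by direct measurement at each scheduled visit, so the main objective is not lost. The conclusion rests on the text alone and on the anatomical fact that the sternal notch lies above any line through the breast. A reference picture showing the whole breast and the notch would remove most of the practical risk, but the sentence beside it would still need correcting. The change is worth making because it costs almost nothing and a missed baseline image cannot be recovered.

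**What to change.** Before the first baseline image is taken:

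1. In the Photography section, replace the framing sentence with a fixed breast frame, for example: *Each image shows the whole of both breasts as far as the view allows; the frontal image also includes the sternal notch and both inframammary folds. Camera distance, height and angle are the same at every visit.*
2. Make the Visit 1 screening text and the reference picture match that sentence.
3. In the Evaluation section, state that the surgeons rate these images, the standard-format Vectra images already being collected, or both.

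The back view may stay or go; it does no harm here.

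**Cost:** a wording change and, if needed, a new reference picture, with the same camera, visits and staff. The one drawback is that images already taken in the old frame would not match the new ones. For any such women, taking both frames at follow-up would keep a matched before-and-after pair.

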Subject Selection	Investigator will determine patient's eligibility to participate in the study according to inclusion/exclusion criteria.

INMODE
aesthetic solutions

Clinical Evaluation of Safety and Efficacy of Radio-Frequency Assisted Lipolysis (RFAL) of Breast Envelope and Nipple-Areolar Complex (NAC) Position

Protocol No:
DO607738A

Rev. Date: August, 2018

SIRB ID: 6254

Study Objectives	The purpose of this study is to evaluate the safety and efficacy of RFAL for the Breast Envelope and Nipple-Areolar Complex (NAC) Position as measured by the Vectra 3D circumferential imaging system (Canfield, NJ).
Main Eligibility Criteria	
Inclusion Criteria
 
• Informed consent agreement signed by the subject.• Healthy females 21 to 60 years of age.• Presence of grade I-III Breast Ptosis, mastopexy with history of breast augmentation, correction of asymmetry, mastopexy alone, mastopexy following implant removal and modest breast reduction in combination with or without lipoaspiration.• Post-menopausal or surgically sterilized or using a medically acceptable form of birth control at least 3 months prior to enrolment and during the entire course of the study (i.e., oral contraceptives, IUD, contraceptive implant, barrier methods with spermicide, or abstinence).• Willingness to follow the treatment and follow-up schedule and the post-treatment care.• All participants must have a recorded mammogram before the beginning of the study. 
Exclusion Criteria
 
• Pacemaker or internal defibrillator, or any other active electrical implant anywhere in the body.

INMODE
aesthetic solutions

Clinical Evaluation of Safety and Efficacy of Radio-Frequency Assisted Lipolysis (RFAL) of Breast Envelope and Nipple-Areolar Complex (NAC) Position

Protocol No:
DO607738A

Rev. Date: August, 2018

SIRB ID: 6254

- Permanent implant in the treated area such as metal plates and screws, silicone implants or an injected chemical substance.
- Current or history of skin cancer (remission of 5 years), or current condition of any other type of cancer, or pre-malignant moles.
- Severe concurrent conditions, such as cardiac disorders, epilepsy, uncontrolled hypertension, and liver or kidney diseases.
- History of bleeding coagulopathies or use of anticoagulants in the last 2 weeks.
- Impaired immune system due to immunosuppressive diseases such as AIDS and HIV or use of immunosuppressive medications.

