- Poorly controlled endocrine disorders, such as diabetes or thyroid dysfunction.
- Any active condition in the treatment area, such as sores, psoriasis, eczema, and rash.
- History of skin disorders, keloids, abnormal wound healing, as well as very dry and fragile skin.
- Use of Isotretinoin (Accutane®) within 6 months prior to treatment.
- Significant systemic illness or occult systemic illness.
- Illness, infection or skin diseases localized in area of treatment.
- Other therapies or medication which may interfere with treatment.
- Breastfeeding, pregnant, or planning to become pregnant during the study.
- Allergy to lidocaine or other anaesthesia.

INMODE
aesthetic solutions

Clinical Evaluation of Safety and Efficacy of Radio-Frequency Assisted Lipolysis (RFAL) of Breast Envelope and Nipple-Areolar Complex (NAC) Position

Protocol No:
DO607738A

Rev. Date: August, 2018

SIRB ID: 6254

	
• Recent surgery in treatment area within the past 6 months.• Participation in a study of another device or drug within 3 months prior to enrolment or during this study.• As per the Investigator's discretion, any physical or mental condition which might make it unsafe for the patient to participate in this study.• As per the practitioner's discretion, refrain from treating any condition that might make it unsafe for the patient.
Risk to the Subject	
Risks involved with study participation, include:
 
1. Pain2. Excessive swelling (Edema)3. Excessive skin redness (Erythema)4. Bleeding5. Bruising6. Burn7. Blistering8. Crusting9. Scarring10. Skin pigmentation, textural, and/or contour alterations11. Infection12. Asymmetry13. Temporary injury to nerves (neuropraxia) where nerve branches are superficial

I N M O D E
aesthetic solutions

Clinical Evaluation of Safety and Efficacy of Radio-Frequency Assisted Lipolysis (RFAL) of Breast Envelope and Nipple-Areolar Complex (NAC) Position

Protocol No:
DO607738A

Rev. Date: August, 2018

SIRB ID: 6254

Scope and Duration of the Study

The clinical study will include up to 10 subjects at one site. Eligible subjects will receive single treatment according to the study protocol and will be followed up for a period of up to 1 year to document treatment safety and efficacy.

DEVICE DESCRIPTION

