The InModeRF is a Radio-Frequency device comprising of the following main modules:

- AC/DC power supply isolating system modules from AC voltage
- RF generator providing output of RF power to the hand piece
- Microcontroller controlling RF output, monitoring tissue electrical parameters, skin surface temperature and proper functioning of electronic modules.

InModeRF DEVICE

Hand piece delivers RF power to the subject and has the following main elements

- Internal electrode insulated with Teflon with a treatment tip at the distal end
- External electrode with temperature sensor
- Mechanism adjusting distance between electrodes

[figure not shown]
I N M O D E
aesthetic solutions

Clinical Evaluation of Safety and Efficacy of Radio-Frequency Assisted Lipolysis (RFAL) of Breast Envelope and Nipple-Areolar Complex (NAC) Position

Protocol No:
DO607738A

Rev. Date: August, 2018

SIRB ID: 6254

HAND PIECE

Principles of operation

Operation of InModeRF device is based on the concept of a minimally invasive procedure. The hand piece is comprised of two electrodes where an internal electrode is inserted into subcutaneous fat layer and its size is designed for thermal destruction of adipose tissue with RF energy. A second external electrode is applied to the skin surface. Both electrodes have a rigid connection with an adjustable distance between them. RF power and tip size of the internal electrode are designed to liquefy fat in the vicinity of the electrode tip. The external electrode has a much larger area that creates much lower power density on the skin of the patient. The RF current flows from the internal electrode to the external electrode. The hand piece can monitor both tissue impedance and temperature in real time. The outer temperature measurement acts as safety mechanism that stops the RF current in the case the skin temperature is reaches the desire temperature set by the doctor. The figure below shows RF energy distribution in tissue between electrodes.

[figure not shown]
I N M O D E
aesthetic solutions

Clinical Evaluation of Safety and Efficacy of Radio-Frequency Assisted Lipolysis (RFAL) of Breast Envelope and Nipple-Areolar Complex (NAC) Position

Protocol No:
DO607738A

Rev. Date: August, 2018

SIRB ID: 6254

RF energy distribution between electrodes

STUDY DESIGN

Prospective, self-controlled, open label, single arm clinical study

CLINICAL PROCEDURE

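### Nothing in the available text masks the three photograph raters to which image is postoperative, so this supporting rating is open to a shared expectation bias that coding and shuffling the images would cheaply reduce

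*Combined protocol and SAP*

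**What the plan says.** The Evaluation section gives the panel one sentence: "Three independent plastic surgeons will evaluate photographs of the preoperative and postoperative photographs at 3-, 6- and if applicable, 12-month results". It does not say what the surgeons know about each image, in what order they see the images, or whether they rate 2D photographs or Vectra output.

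Under Safety and Result Measurements, the Photography section requires four views per time point (front, back and two sides) and adds: "Each picture should be accompanied with the date, visit number, subject ID, subject initials". It also standardises the set-up: "The photos should be taken under controlled conditions, including the colour of the background material, distance from the camera, angle and lighting". The Vectra 3D Photography section separately produces photographs in two formats.

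Study Design reads "Prospective, self-controlled, open label, single arm clinical study". Scope and Duration caps enrolment: "The clinical study will include up to 10 subjects at one site". The synopsis objective is to evaluate the treatment "as measured by the Vectra 3D circumferential imaging system (Canfield, NJ". Data Analysis promises descriptive statistics and unnamed comparison tests. The 5-point scale under Visit 3 belongs to the patient and physician satisfaction forms, not to the panel.

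**The concern.** With no control arm, before versus after is the main contrast. A rater who knows which image is the later one may lean toward seeing improvement, and there is no comparison group in which the same lean would appear and cancel.

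The patients and the treating physician necessarily know that treatment was given. The panel is the one assessment the available text gives to raters described as independent. Independence says who rates, not what they know. Without masking, much of the reason for using outside raters is lost.

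The Treatment Parameters Study section also lets power and duration differ between the right and left breast, and nothing available keeps that from the surgeons.

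**Working it through.** **Is there masking?** The plan states no figure to reproduce, so the first step is to set the sections side by side.

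| Section | What it settles | What it leaves open |
|---|---|---|
| Evaluation | three surgeons, which time points | masking, order, coding, scale, type of photograph |
| Photography | labels on each 2D picture, four views, standard conditions | whether rating copies keep the labels |
| Study Design | open label, single arm | any exception for the raters |
| Data Analysis | descriptive statistics, unnamed tests | how three readings are combined |

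Either the date or the visit number shows which picture came later. Standard lighting and distance reduce technical differences but do not hide the order.

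**Comparisons exposed (maxima).** Subjects × surgeons × follow-up time points:
- 10 × 3 × 2 = 60, or 10 × 3 × 3 = 90 with 12 months.
- If only 5 enrol: 5 × 3 × 2 = 30, or 5 × 3 × 3 = 45.

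**Why averaging and more subjects do not help.** Write surgeon j's score for subject i as true change + b + error, where b is the shared lean. The mean over surgeons and subjects has expectation (true change + b) for any number of either. Only the error variance shrinks.

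**Illustration only.** The lean, the SD and both decision rules below are assumptions, not taken from the documents. True change is zero throughout.

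1. *Forced choice.* One surgeon picks the better image in 10 pairs and favours the later image with probability p. P(at least 9 of 10) = 10·p⁹·(1−p) + p¹⁰. This is 1.1% at p = 0.5 (no lean), and 4.6%, 14.9% and 37.6% at p = 0.6, 0.7 and 0.8.
2. *Score.* Take b in SDs of the per-subject score and a two-sided 5% one-sample t test. The chance of a false improvement is the upper tail of a noncentral t with n − 1 degrees of freedom and noncentrality b√n, beyond t(0.975, n − 1).

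| n | b = 0 | b = 0.25 | b = 0.5 | b = 1.0 |
|---|---|---|---|---|
| 5 | 2.5% | 6.4% | 13.9% | 40.1% |
| 10 | 2.5% | 10.6% | 29.3% | 80.3% |

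At b = 0.5 the rate is 13.9%, 29.3% and 56.5% for n = 5, 10 and 20. More subjects make a shared lean look more certain.

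3. *Imperfect masking.* Suppose a shuffled set holds a baseline and two follow-ups. Each of three surgeons separately identifies the baseline in a share q of sets, a wrong guess falls equally on the two follow-ups, and the median lean of the three applies. By simulation with b = 0.5 and n = 10, the false-improvement rate is about 2.5% at q = 1/3 (chance), 7% at q = 0.5, 20% at q = 0.75 and 29% at q = 1. Partial masking helps, but much less once most baselines are recognised.

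**Workload of the fix (maxima).** Subjects × surgeons × images per subject, for one camera view:
- 10 × 3 × 3 = 90, or 10 × 3 × 4 = 120 with 12 months.
- If all four views are rated: 90 × 4 = 360, or 120 × 4 = 480.

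**The case against.** **The point rests on silence.** Part of the protocol between Records and Reports and Appendix I is not available, and the case report form is not in the file, although the Screening section relies on it for "as well as additional information that is specified in the case report form". A masking step or a scale could be there. This stands as a limit: the claim covers the available text only.

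**The type of photograph is not stated.** The labelling rule stands under 2D Photography. If the surgeons rate Vectra photographs, it does not apply directly, and the split between named measure and supporting rating is less clean. This also stands. The absence of masking does not depend on it, and the fix asks for the choice to be stated.

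**The rates use invented inputs.** Correct. They show direction only. That unmasked before-and-after rating can be biased needs no simulation.

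**Masking may fail.** Access-port marks or a visible change may reveal the later image, although the treatment recommendations place the ports usually in inconspicuous areas. This limits the gain without removing it.

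**Stronger readings that the documents do not support.** A reader might infer that labelled pictures are handed to the surgeons; the text says only that pictures carry labels. A reader might infer that the study's efficacy result as a whole is biased; the objective names Vectra 3D, and static measurements add to it. A reader might also suspect that pen marks reveal a treatment-day baseline image, but the Screening section says "Photographs should be taken prior to the baseline treatment and at each of the follow-up visits", and marking belongs to the treatment steps.

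**Conclusion.** The concern holds in a limited form. As written, the plan leaves three surgeons free to know which image is postoperative, in a design with no control arm to absorb a shared expectation. Up to 60 comparisons are exposed, or 90 with 12 months.

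The amount of bias cannot be estimated from the documents, and they do not show that any bias will occur. Calling the rating supporting is an inference from the objective, because no hierarchy of endpoints is stated. The conclusion also assumes that the unavailable text and the case report form contain no masking step. This is a cheap improvement worth making before the first reading, not a flaw that invalidates the study.

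**What to change.** Add to the Evaluation section:

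> In the copies shown to the surgeons, the date, the visit number and all subject identifiers are removed and replaced by a random code. For each subject, baseline and follow-up photographs of the same view are shown in random order, to each surgeon independently. Surgeons are not told the time point or the treatment parameters. They use one scale fixed before the first reading, and scores are locked before unmasking.

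State also whether 2D or Vectra photographs are rated and which of the four views are used, for example those that show the nipple-areolar complex. Source files keep their labels. If the case report form already holds a scale or a masking step, refer to it.

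**Cost.** Protocol wording and image preparation, with no extra raters, visits or subjects. The workload is up to 90 image views per rated view (120 with 12 months), or 360 (480) if all four views are rated. The downsides are that ratings wait until follow-up is complete, masking may be partial, and the result may be less favourable.
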